3.5.1. Summary of pre-randomisation actions

Event	Measurement/Action	Means	Timing	Time
Recruit participants	Inform participants	Participant Information Sheet	At time of recruitment	5-10 minutes
Consent participants	Informed written consent	Online consent form	At time of consent	5 minutes
Demographic data collection	Age, gender, ethnicity, education level	Online questionnaire	Once consented	2-3 minutes
Health Literacy Assessment	Newest Vital Sign-UK	Online questionnaire	Once consented	3-5 minutes

3.5.2. Summary of Study Outcome Measurement

Outcome	Data	Measurement Tool	Timing	Time
Primary Outcome	Participant satisfaction	Client Satisfaction questionnaire (CSQ-8)	Following intervention	3 minutes
Secondary Outcomes	Knowledge, attitudes and practices towards general and regional anaesthesia	KAP questionnaire	Following intervention	5-10 minutes
	Stated preference of anaesthetic technique	KAP questionnaire	Following intervention	<1 minute

3.6. WITHDRAWAL CRITERIA

Each participant has the right to withdraw at any time. If a participant withdraws, we will continue to analyse any data already collected, unless the participant expresses a wish for any associated data to be destroyed.

4. ADVERSE EVENTS

4.1. DEFINITIONS

Adverse Event (AE): any untoward medical occurrence in a patient or clinical study subject.

Serious Adverse Event (SAE): any untoward and unexpected medical occurrence or effect that:

- **Results in death**
- **Is life-threatening** – *refers to an event in which the subject was at risk of death at the time of the event; it does not refer to an event which hypothetically might have caused death if it were more severe*
- **Requires hospitalisation, or prolongation of existing inpatients' hospitalisation**
- **Results in persistent or significant disability or incapacity**
- **Is a congenital anomaly or birth defect**

Medical judgement should be exercised in deciding whether an AE is serious in other situations. Important AEs that are not immediately life-threatening or do not result in death or hospitalisation but may jeopardise the subject or may require intervention to prevent one of the other outcomes listed in the definition above, should also be considered serious.

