4.2. REPORTING PROCEDURES

All adverse events should be reported. Depending on the nature of the event the reporting procedures below should be followed. Any questions concerning adverse event reporting should be directed to the Chief Investigator in the first instance.

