4.2.1 Non serious AEs

All such events, whether expected or not, should be recorded- it should be specified if only some non-serious AEs will be recorded, any reporting should be consistent with the purpose of the trial end points.

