4.2.2 Serious AEs

An SAE form should be completed and emailed to the Chief Investigator within 24 hours.

All SAEs should be reported to the North West London REC where in the opinion of the Chief Investigator, the event was:

- 'related', ie resulted from the administration of any of the research procedures; and
- 'unexpected', ie an event that is not listed in the protocol as an expected occurrence

Reports of related and unexpected SAEs should be submitted within 15 days of the Chief Investigator becoming aware of the event, using the NRES SAE form for non-IMP studies. The Chief Investigator must also notify the Sponsor of all related and unexpected SAEs.

Local investigators should report any SAEs as required by their Local Research Ethics Committee, Sponsor and/or Research & Development Office.

Contact details for reporting SAEs

[contact]

CI email (and contact details below)

Please send SAE forms to: [name] ([contact])

[contact] (Mon to Fri 09.00 – 17.00)

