5. ASSESSMENT AND FOLLOW-UP

Baseline demographic data will be collected for all study patients. These will include age, gender, ethnicity and educational level.

Assessment will be carried out using the following tools:

- CSQ-8 satisfaction questionnaire (appendix 12.1)
- Newest Vital Sign (NVS)-UK (appendix 12.2)
- Knowledge, Attitudes and Practice questionnaire (appendix 12.3), based on information contained in the consent process

Each participant, with their consent, will be informed of the outcome of the trial and any subsequent publication. There is no requirement for follow-up after the investigative period.

There is unlikely to be any losses as the participant will undertake the 2 questionnaires and state their theoretical choice of anaesthesia immediately after undergoing either the traditional verbal consent process and/ or the video-assisted consent process. The only possible loss would be if the participants abruptly withdraws consent to participate if called away for clinical or personal reasons.

The end of the trial will be when the trial database is complete and locked for analysis.

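### Section 4.1 builds expectedness into the SAE definition, while section 4.2.2 makes it a later Chief Investigator judgement on events that are already SAEs; the two must be reconciled.

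*Combined protocol and SAP*

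**What the plan says.** Section 4.1 defines an adverse event with no expectedness condition: "any untoward medical occurrence in a patient or clinical study subject". It then defines an SAE as "any untoward and unexpected medical occurrence or effect that" leads to one of five listed outcomes. A closing paragraph lets medical judgement class further events as serious. These are described as "Important AEs that are not immediately life-threatening or do not result in death or hospitalisation but may jeopardise the subject", or as events that may need intervention to prevent a listed outcome.

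Section 4.2 sets the general duty: "All adverse events should be reported". The procedure then depends on the nature of the event. Section 4.2.1, headed for non-serious events, has them recorded regardless of expectedness.

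Section 4.2.2 requires an SAE form to reach the Chief Investigator within 24 hours. It continues: "All SAEs should be reported to the North West London REC where in the opinion of the Chief Investigator, the event was" both related and unexpected. It defines the second term as "unexpected', ie an event that is not listed in the protocol as an expected occurrence". The Chief Investigator must also tell the Sponsor of SAEs that meet both conditions.

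**The concern.** Seriousness, relatedness and expectedness are three separate questions. Section 4.2.2 keeps them separate: the event is serious, so a form is sent, and the Chief Investigator then judges the other two. Section 4.1 puts expectedness into the first step, where whoever first sees the event classifies it.

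An illustration, not taken from the documents: a participant faints during the acted video, falls and is admitted to hospital. A team member who thinks fainting at medical footage is foreseeable could conclude from 4.1 that this is not an SAE. A colleague who relies on 4.2.2 would call the same event unexpected, because the protocol lists nothing as expected, and would send the form. Each has support in the text.

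At stake is whether the 24-hour form is sent and whether the Chief Investigator makes the formal assessment. Reporting to the ethics committee and notification of the Sponsor both follow from that assessment.

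**Working it through.** No arithmetic applies. The check sets the sections side by side.

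**1. Does the test in 4.2.2 make sense given 4.1?** If every SAE is unexpected by definition, asking whether an SAE was unexpected always gives yes, and the question is empty. If the question is meant to separate some SAEs from others, then some SAEs must be expected, and 4.1 is wrong to exclude them. Both cannot stand. The adverse event definition and 4.2.1 impose no expectedness condition, so the word in the SAE definition is the outlier.

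**2. Where does each kind of event go, read literally?**

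| Event | First reporter's view | SAE under 4.1? | Procedure |
|---|---|---|---|
| Meets a listed serious outcome | Unexpected | Yes | 4.2.2: 24-hour form, then Chief Investigator assessment |
| Meets a listed serious outcome | Expected | No | General duty in 4.2 only; 4.2.2 is not triggered and 4.2.1 is for non-serious events |
| Not serious | Either | No | 4.2.1: recorded |

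The second row has a duty to report but no procedure.

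**3. Does the medical-judgement paragraph close the gap?** Not clearly. It addresses situations other than the listed outcomes, mainly events short of immediate threat to life, death or hospitalisation. Taken literally, a lesser event can be made serious without any expectedness test, while a foreseeable hospitalisation cannot.

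**4. What does *unexpected* mean in 4.1?** Section 4.1 neither defines the word nor refers to 4.2.2. I looked for a list of expected occurrences in sections 1 to 9 and appendices 11.1 to 11.3. The number listed is 0; the anaesthetic complications in appendix 11.3 are questionnaire items. Two readings follow:

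- *The 4.2.2 definition is carried back into 4.1.* With nothing listed, every event is unexpected, and the word in 4.1 excludes nothing.
- *The word has its ordinary sense.* The first reporter's own view decides, and the second row of the table can occur.

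**5. What if a list were added and 4.1 left alone?** Under the first reading the word would then start to exclude events: any serious event on the list would cease to be an SAE. Adding a list therefore does not replace correcting the definition.

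**The case against.** The strongest reply is that nothing is lost. Section 4.2 requires all adverse events to be reported and sends reporting questions to the Chief Investigator. An event judged expected still meets the adverse event definition. This stands, and it limits the point. A reader might infer that a serious event could be dropped before anyone assesses it; the documents do not support that. The event leaves the SAE route, not all reporting.

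The second reply is that the protocol's only definition of *unexpected* is in 4.2.2, and with no list it filters out nothing. This stands if that definition governs 4.1. But 4.1 does not point to it, so the exclusion remains open to a reporter who uses the ordinary sense. It also means that the missing list does not itself cause the exclusion, as a reader might suppose.

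Third, this is a single-centre trial (section 3.2), at two hospitals of one Trust (section 3.3). The Chief Investigator chairs the group that runs it day to day, which includes the whole named research team (section 8). No remote site screens events independently, so the Chief Investigator may well hear of a serious event informally. That lowers the practical risk but does not reconcile the text.

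Finally, safety is neither an objective nor an outcome. A reader might go further and say that a report of no SAEs would be uninterpretable. That does not follow while all adverse events must be reported.

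**Conclusion.** The contradiction between 4.1 and 4.2.2 is real, and the definition is wrong as written. The supportable consequence is narrow: a serious event that the first reporter considers expected remains a reportable adverse event, but can miss the 24-hour form and the Chief Investigator's assessment, and no written procedure covers it. This rests on reading 4.1 literally, with *unexpected* in its ordinary sense.

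The rule applies to all 206 planned participants, but the documents give no event rate, so no count can be estimated. Few events are likely, since both arms watch recorded material and complete questionnaires. The CSQ-8 primary analysis is unaffected.

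Two nearby matters are editorial and not part of this point. Section 4.2.1 retains a template instruction ("it should be specified if only some non-serious AEs will be recorded"), and no adverse event collection window is stated. A reader might infer that the plan promises capture of events through later surgery while nobody is looking. The documents do not say so: section 5 has the questionnaires completed immediately after the consent process and adds "There is no requirement for follow-up after the investigative period". An explicit window would be clearer, but its absence is missing detail and not a contradiction.

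**What to change.** 1. In section 4.1, delete *and unexpected* from the SAE definition, so that seriousness alone defines an SAE.
2. In section 4.2.2, leave relatedness and expectedness as the Chief Investigator's judgement on events already reported as SAEs. No change of wording is needed for this.
3. The sponsor should either list the occurrences regarded as expected or confirm that there are none. The documents do not settle which, so the review should not supply the statement that no SAE is expected. If a list is added, the deletion in 4.1 must be made too, for the reason in step 5 of the working.

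The cost is two deleted words and one short list or statement. The downside is at most a few extra SAE forms, with no added visits or staff and no change to the analysis.

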4.2. REPORTING PROCEDURES

All adverse events should be reported. Depending on the nature of the event the reporting procedures below should be followed. Any questions concerning adverse event reporting should be directed to the Chief Investigator in the first instance.

4.2.1 Non serious AEs

All such events, whether expected or not, should be recorded- it should be specified if only some non-serious AEs will be recorded, any reporting should be consistent with the purpose of the trial end points.

4.2.2 Serious AEs

An SAE form should be completed and emailed to the Chief Investigator within 24 hours.

All SAEs should be reported to the North West London REC where in the opinion of the Chief Investigator, the event was:

- 'related', ie resulted from the administration of any of the research procedures; and
- 'unexpected', ie an event that is not listed in the protocol as an expected occurrence

Reports of related and unexpected SAEs should be submitted within 15 days of the Chief Investigator becoming aware of the event, using the NRES SAE form for non-IMP studies. The Chief Investigator must also notify the Sponsor of all related and unexpected SAEs.

Local investigators should report any SAEs as required by their Local Research Ethics Committee, Sponsor and/or Research & Development Office.

Contact details for reporting SAEs

[contact]

CI email (and contact details below)

Please send SAE forms to: [name] ([contact])

[contact] (Mon to Fri 09.00 – 17.00)

5. ASSESSMENT AND FOLLOW-UP

Baseline demographic data will be collected for all study patients. These will include age, gender, ethnicity and educational level.

Assessment will be carried out using the following tools:

- CSQ-8 satisfaction questionnaire (appendix 12.1)
- Newest Vital Sign (NVS)-UK (appendix 12.2)
- Knowledge, Attitudes and Practice questionnaire (appendix 12.3), based on information contained in the consent process

Each participant, with their consent, will be informed of the outcome of the trial and any subsequent publication. There is no requirement for follow-up after the investigative period.

There is unlikely to be any losses as the participant will undertake the 2 questionnaires and state their theoretical choice of anaesthesia immediately after undergoing either the traditional verbal consent process and/ or the video-assisted consent process. The only possible loss would be if the participants abruptly withdraws consent to participate if called away for clinical or personal reasons.

The end of the trial will be when the trial database is complete and locked for analysis.

6. STATISTICS AND DATA ANALYSIS

Two hundred and six patients in total will be randomised using an online randomisation tool. <https://www.graphpad.com/quickcalcs/randomize1.cfm>

Patient satisfaction, the primary endpoint measured by CSQ-8, is expected to be approximately 30 in both arms. VAC and SVC will be considered equivalent if the VAC satisfaction score is no more than 1.5 points lower than the SVC score. With 103 subjects in the Control Group (SVC) and 103 subjects in Experimental Group (VAC), there is an 85% chance that the observed difference (SVC-VAC) in satisfaction scores will be significantly less than 1.5 at the 5% level, if the true means are 30 in both groups. The standard deviation has been assumed to be 4.

After the first 50 participants have been entered into the trial a feasibility analysis will be undertaken. Three outcomes of particular interest will be the accrual rate, the proportion accepting their randomisation and the proportion evaluable (completing all questionnaires). With 50 participants it will be possible to estimate the proportions in the latter two groups with 95% confidence intervals of at most $\pm 15\%$. A record will be kept of the number of participants approached and their reasons for declining to enter the study. With 50 participants it should be possible to identify and remedy any minor issues that are impediments to recruitment. It may be necessary to plan to increase accrual if withdrawals or the number of non-evaluable participants is greater than expected.

The primary analysis will be by intention to treat (ITT). It is planned to make comparisons between groups for normally distributed variables with independent samples t-test or ANOVA, variables that are not normally distributed will be analysed with Mann–Whitney U-tests. The Chi-squared or Fisher's exact test will be used to compare proportions and Pearson Product or Spearman Rank statistics will be used to assess correlation. Multiple regression exploratory analyses may be employed to estimate multiple effects simultaneously.

Data and all appropriate documentation will be stored for a minimum of 5 years after the completion of the study, including the follow-up period.

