2. STUDY OBJECTIVES

- The aim of this study is to determine if the use of video assisted consent during the anaesthetic consent process, for both GA and RA, affects the participants' satisfaction, knowledge of, and attitudes towards, anaesthesia.
- We hypothesise that using video media will improve participant knowledge, understanding and satisfaction of the anaesthetic consent process, thereby resulting in better quality informed consent.

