11. APPENDICES

11.1. CLIENT SATISFACTION QUESTIONNAIRE (CSQ-8)

The Client Satisfaction Questionnaire (CSQ) instruments are self-report questionnaires constructed to measure satisfaction with services received by individuals²⁹.

The CSQ-8 is an 8-item questionnaire that measures the most salient items for the measurement of satisfaction with services:

Questionnaire Item	Scoring			
	4	3	2	1
How would you rate the quality of the service you received?	Excellent	Good	Fair	Poor
Did you get the kind of service you wanted?	Yes definitely	Yes generally	No not at all	No definitely not
To what extent has our service met your needs?	Almost all met	Most met	Only a few met	None met
If a friend were in need of similar help would you recommend our service?	Yes definitely	Yes I think so	No I do not think so	Definitely not
How satisfied are you with the amount of help you received?	Very satisfied	Mostly satisfied	Indifferent	Quite dissatisfied
Have the services you received helped you to deal more effectively with your problems?	Yes a great deal	Yes somewhat	No did not help	No made it worse
In an overall sense, how satisfied are you with the service you have received?	Very satisfied	Mostly satisfied	Indifferent	Quite dissatisfied
If you were seeking help again, would you come back to our service?	Yes definitely	Yes I think so	No I do not think so	No definitely not

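### The trial is sized on a 1.5-point CSQ-8 margin, but the analysis plan never tests that margin, and its normality rule would very likely send CSQ-8 to Mann–Whitney.

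*Combined protocol and SAP*

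**What the plan says.** Section 6 (Statistics and data analysis) has two parts bearing on the primary endpoint.

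- **Sizing paragraph.** The criterion is "VAC and SVC will be considered equivalent if the VAC satisfaction score is no more than 1.5 points lower than the SVC score". With 103 per arm, true means of 30 in both arms and SD 4, it gives an 85% chance that "the observed difference (SVC-VAC) in satisfaction scores will be significantly less than 1.5 at the 5% level". It does not say whether the 5% is one-sided or two-sided.
- **Analysis paragraph.** It opens with "The primary analysis will be by intention to treat (ITT"), then: "It is planned to make comparisons between groups for normally distributed variables with independent samples t-test or ANOVA", and "variables that are not normally distributed will be analysed with Mann–Whitney U-tests". It does not mention CSQ-8, the 1.5 margin, a non-zero null value, a confidence limit or sidedness, and it gives no criterion for judging normality.

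Two other places matter. Section 2 (Study objectives) states a different hypothesis: "We hypothesise that using video media will improve participant knowledge, understanding and satisfaction of the anaesthetic consent process". Appendix 11.1 says "The CSQ-8 is an 8-item questionnaire" and scores each item from 1 to 4, so a summed score runs from 8 to 32. No other section links the margin to an analysis.

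**The concern.** The success criterion and the sample size both concern a difference in means measured against 1.5. The analysis paragraph offers generic between-group comparisons chosen by distribution. A t-test could serve the margin through a shifted null or its confidence interval, but the plan does not say that it will. Mann–Whitney compares ranks and, as named, yields nothing to hold against a 1.5-point mean margin.

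If the plan is followed as written, the primary analysis probably would not produce the quantity on which success is defined. The estimator, the decision rule and the choice between a margin claim and an improvement claim would then be settled after the data are seen.

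**Working it through.** **Inputs.** Section 6: margin 1.5, SD 4, true difference 0, 103 per arm, 5% level, 85% power. Appendix 11.1: 8 items × 4 = maximum 32.

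**1. Reproduce the stated power.** SE = 4 × √(2/103) = 0.557, and 1.5/0.557 = 2.691.

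| Reading of the 5% level | Calculation (normal) | Power |
|---|---|---|
| One-sided 5% | Φ(2.691 − 1.645) | 85.2% (t: 85.0%) |
| One-sided 2.5% | Φ(2.691 − 1.960) | 76.8% (t: 76.4%) |
| Two-sided equivalence, 5% each side | 2Φ(1.046) − 1 | 70.5% |

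Only a one-sided 5% test of means against 1.5 gives the stated 85%. The sizing is therefore a non-inferiority calculation on means, and it is correct as such.

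**2. Would the normality rule select Mann–Whitney?** The ceiling lies (32 − 30)/4 = 0.5 SD above the planned mean. A normal curve would put 1 − Φ(0.5) = 30.9% of scores above 32, which is impossible.

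A bound holds for any shape. Let Z = (score − 30)/4, so Z ≤ b = 0.5. Then E[(b − Z)(Z − c)²] ≥ 0 for every c, which gives skewness ≤ b + 2c + bc². At c = −1/b this is b − 1/b = 0.5 − 2 = **−1.5**.

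As an illustration, a beta-binomial on 8–32 with mean 30 and SD 4 puts 62% of scores at 32 and has skewness −2.6. Shapiro–Wilk at 5% (an assumed criterion) rejected normality in 100% of simulated samples of 103 at mean 30 with SD 4, 3 or 2 and at mean 28 with SD 4. At mean 26, SD 4, it rejected in about 99% or more.

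**3. Does Mann–Whitney track the margin?** Simulation: SVC as in the beta-binomial above, 103 per arm, 10,000 trials, two-sided 5% Mann–Whitney. The margin test uses a one-sided 95% unequal-variance t-limit. The VAC shapes are assumptions. The rows marked BB are beta-binomials with a lower mean, not pure location shifts; in the first, for example, the share at 32 falls from 62% to 27.5%.

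True deficit 1.5 (at the margin):

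| VAC scores | Mann–Whitney non-significant | Margin test wrongly passes |
|---|---|---|
| BB, SD 4 | 0.3% | 4.5% |
| BB, SD 4.6 | 4.3% | 5.2% |
| 8.3% of patients at 12 (0.083 × 18 = 1.5) | 78.6% | 6.0% |

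True deficit 0.5 (inside the margin):

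| VAC scores | Mann–Whitney significant | Significant and margin met |
|---|---|---|
| BB, SD 4 | 42.9% | 9.2% |
| BB, SD 4.3 | 24.5% | 2.4% |
| Half of patients down 1 point | 88.1% | 44.8% |
| 2.8% of patients at 12 (0.028 × 18 = 0.5) | 6.8% | 1.0% |

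Mann–Whitney can miss a deficit as large as the margin, and can be significant when the deficit is acceptable. With equal arms, the mean-based test kept about 85% power despite the skew.

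**4. If the t-test were kept but used against zero.** At a true 1.5 deficit, a two-sided 5% t-test is non-significant in Φ(1.960 − 2.691) = 23% of trials (23.6% by t). Reading that as equivalence, which the plan does not propose, would give an error of about 24% instead of 5%.

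**The case against.** The strongest reply is that section 6 already contains most of a decision rule: endpoint, direction, margin, level and criterion appear in the sizing paragraph, and the later list of tests can be read as generic guidance for all variables. That is a fair reading, and it narrows the defect. But the paragraph that introduces the primary analysis does not adopt the rule, states no estimator, limit or sidedness, and does not exempt CSQ-8 from the switch.

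Other points:

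- **Normality is not defined.** A visual check, or observed scores unlike the planning values, could keep the t-test. This stands, so the route to Mann–Whitney is very likely rather than certain. A t-test of zero difference would still leave the margin untested.
- **A rank-based margin analysis exists**, by shifting scores 1.5 points or using a Hodges–Lehmann interval. True, but the plan names neither, and both target a location shift rather than the mean difference used for sizing.
- **The simulated sizes rest on invented shapes.** This stands. The 79% needs a small VAC subgroup scoring very low, which raises the VAC SD to about 6.3 (√(0.917 × 16 + 0.083 × 0.917 × 18²)). The range shows that the two analyses can disagree; it does not predict this trial.
- **A significant Mann–Whitney result at a 0.5 deficit detects a real difference**, and lower but within the margin is a legitimate finding. Correct. The difficulty is that the plan does not say which result decides.

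**Conclusion.** The concern holds and must be fixed, because it affects the decision rule for the primary endpoint. The sample size is sound for a one-sided 5% comparison of means. The gap is that the analysis paragraph does not carry that comparison forward, and its own rule would very likely replace it with a rank test.

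The skewness bound of -1.5 is exact given mean 30, SD 4 and a summed score capped at 32. The prediction that Mann–Whitney would be chosen also needs a normality check that responds to such skewness. The practical consequence cannot be pinned to one figure: at a true 1.5-point deficit, Mann–Whitney was non-significant in anything from 0.3% to 79% of trials, depending on the assumed shape. The section 2 improvement hypothesis adds to the ambiguity, because nothing orders it relative to the margin test.

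**What to change.** Exempt CSQ-8 from the normality switch and add wording such as:

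> The primary analysis estimates the mean CSQ-8 difference, SVC minus VAC, whatever the distribution, with an unequal-variance t-interval and a bootstrap interval as a check. Non-inferiority is concluded if the upper one-sided 95% confidence limit is below 1.5, matching the level used for the sample size. If non-inferiority is shown, the improvement hypothesis in section 2 is tested by a two-sided zero-difference test of the same mean difference. Mann–Whitney is a sensitivity analysis. A non-significant difference test is not evidence of equivalence.

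The word equivalent in the sizing paragraph should become non-inferior, since the criterion runs in one direction only.

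**Cost.** A few lines of text, agreed before any comparison by arm. At one-sided 5% the total stays at 206. If one-sided 2.5% were preferred, power at 103 per arm would be about 76%, and 85% power would need about 129 per arm (128 by normal approximation: 2 × 16 × (1.960 + 1.036)²/1.5² = 127.7).
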